- Low-contrast Sloan letter chart (LCSLC) Vision Test at Baseline/Day 1 (Week 26 of Study HZNP-ACT-301) and post-dose at Week 26 (or PW).
- For all subjects with a normal audiogram result at Screening in Study HZNP-ACT-301, Listening in Spatialized Noise-Sentences Auditory Test (LiSN-S) at Baseline/Day 1 (Week 26 of Study HZNP-ACT-301) and post-dose at Week 26 (or PW).
- Frataxin protein levels in whole blood, muscle biopsies (optional), and buccal cells at Baseline/Day 1 (Week 26 of Study HZNP-ACT-301) and post-dose at Weeks 13 and 26 (or PW).
- Functional staging of ataxia at Baseline/Day 1 (Week 26 of study HZNP-ACT-301), and post-dose at Weeks 13 and 26 (or PW).
- Physician Global Assessment and Patient Global Assessment at Baseline/Day 1 (Week 26 of Study HZNP-ACT-301) and post-dose at Weeks 13 and 26 (or PW).

Quality of Life Assessments

- Quality of life assessments (Modified Fatigue Impact Score [MFIS], and Pediatric Quality of Life [PedsQL] questionnaire or 36-item short-form health survey [SF-36]) at Baseline/Day 1 (Week 26 of Study HZNP-ACT-301) and Weeks 13 and 26 (or PW). The MFIS will be completed for all subjects. Subjects who completed the PedsQL during Study HZNP-ACT-301 will continue to complete the PedsQL in this study. Subjects who completed the SF-36 during Study HZNP-ACT-301 will continue to complete the SF-36 in this study.

Statistical Analyses:

All summaries will be presented by both the treatment received in HZNP-ACT-301 as well as overall.

Safety Endpoints

Adverse event and concomitant medication data will be summarized. Clinical laboratory safety data, vital sign data, echocardiogram data, and ECG interval data will be summarized with descriptive statistics for Baseline, post-dose, and change from Baseline to post-dose values. Shift tables will be presented for clinical laboratory values and ECG categorical results from Baseline to each post-dose visit. Physical examination findings will be listed by subject. Results of immunogenicity testing will be presented in tabular format.

Efficacy Endpoints

The primary efficacy endpoint is the observed change from Baseline to Week 26 for all subjects and from Baseline of HZNP-ACT-301 to Week 26 of HZNP-ACT-302 (52-week treatment duration) for subjects receiving active treatment in both studies in the FARS-mNeuro score. Results will be summarized descriptively.

Secondary Efficacy Endpoints

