2.2 Study Endpoints

The analysis for this study is for an abbreviated safety Clinical Study Report (CSR). All efficacy endpoints mentioned in the protocol have been removed and noted as changes to the planned analyses.

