4.2 Final Analysis

All final, planned analysis identified in the protocol and in this SAP will be performed after the last subject has completed the Follow-up Safety Visit and all relevant study data have been processed and integrated into the analysis data base.

Any post-hoc, exploratory analysis completed to support planned study analysis, which were not identified in this SAP, will be documented and reported in appendices to the CSR. Any results from these unplanned analyses (post-hoc) will also be clearly identified in the text of the CSR.

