6. GENERAL ISSUES FOR STATISTICAL ANALYSIS

Data processing, tabulation of descriptive statistics, calculation of inferential statistics, and graphical representations will be performed using SAS® Software (release 9.3 or higher) for Windows, unless otherwise specified.

Continuous (quantitative) variables will be summarized using descriptive statistics including number of non-missing values, mean, standard deviation (SD), median, minimum, and maximum.

Categorical (qualitative) variables will be summarized using the number and proportion of each possible value. In general, the denominator for the percentage calculation will be based upon the total number of subjects in the study population for the treatment group.

The minimum and maximum will be reported with the same degree of precision (i.e., the same number of decimal places) as the raw data. Measures of location (mean and median) will be reported to 1 degree of precision more than the raw data and measures of spread (standard deviation) will be reported to two degrees of precision more than the raw data.

Assessments done on unscheduled visits will not be summarized but will be listed. All analyses will be completed on the Safety Population unless otherwise specified. Additionally, all summaries will be presented by overall treatment.

All final, planned analyses identified in the protocol and in this SAP will be performed after all relevant study data have been processed and integrated into the analysis database, analysis populations have been finalized, and the database has been locked. Any post-hoc, exploratory analysis completed to support planned study analyses, which were not identified in this SAP, will be documented and reported in Section 9.8 of the CSR. Any results from these unplanned analyses (post-hoc) will also be clearly identified as subject in the text of the CSR.

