9.1 Adverse Events

Missing and partially missing AE start and/or stop dates will be imputed for the purpose of statistical analysis, according to the specifications described in Section 6.1.

A summary of overall TEAEs, TEAEs, SAEs, TEAEs leading to PW, TEAEs by relationship to study drug, and severity of TEAEs will be presented by overall treatment.

Summaries and incidence rates (frequencies and percentages) of individual TEAEs by MedDRA System Organ Class (SOC) and preferred term will be displayed by overall treatment received. Such summaries will be displayed for TEAEs, SAEs, TEAEs leading to early termination, TEAEs by relationship to study drug, and TEAEs by severity

Each subject will be counted only once within each preferred term. If a subject experiences more than one TEAE within a preferred term only the TEAE with the strongest relationship or the maximum intensity, as appropriate, will be included in the summaries of relationship and intensity. No inferential statistical tests will be performed.

In the AE data listings, all AEs will be displayed. AEs that are not treatment-emergent will be flagged.

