9.2 Clinical Laboratory Evaluations

Descriptive summaries of actual (absolute) values and changes from baseline will be presented for Chemistry, Urinalysis, Complete Blood Count, PR, INR, and aPTT. These tables will be grouped by visit, and overall treatment.

The number and proportion of subjects with clinical laboratory values below, within, or above normal ranges, at each study visit will be tabulated (shift tables) for each clinical laboratory analyte by treatment group. Normal ranges will be provided by the central laboratory (URMC) used in this study.

Laboratory values will be displayed in data listings and those that are outside the normal range will be flagged, along with the corresponding normal ranges.

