9.2.1 Immunogenicity Testing

Frequency and percentages of positive anti-drug antibodies (ADA) and neutralizing antibodies (NAb) will be summarized by scheduled visit, and overall treatment received. Additionally, immunogenicity data will be presented in a data listing.

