10. CHANGES FROM PLANNED ANALYSIS

All efficacy analyses has been removed from the study as described in the protocol.

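### The SAP groups safety summaries by overall treatment and drops, without declaring it, the protocol's split by treatment received in HZNP-ACT-301

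*SAP*

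**What the plan says.** Protocol section 2 (Synopsis, Statistical Analyses) sets two layers of presentation: "All summaries will be presented by both the treatment received in HZNP-ACT-301 as well as overall". Protocol section 9.6 neither repeats nor contradicts this.

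SAP section 6 gives the general rule as "Additionally, all summaries will be presented by overall treatment". The same or similar wording is used for disposition (7.1), prior medications and baseline physical examination (7.3), laboratory values (9.2), vital signs (9.3), ECG (9.4), concomitant medication (9.5) and exposure and compliance (9.6). For adverse events (9.1), incidence by system organ class and "preferred term will be displayed by overall treatment received". For immunogenicity (9.2.1): "Frequency and percentages of positive anti-drug antibodies (ADA) and neutralizing antibodies (NAb) will be summarized by scheduled visit, and overall treatment received". Laboratory shift tables are produced "for each clinical laboratory analyte by treatment group", with the group left undefined.

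SAP section 10 consists of one sentence: "All efficacy analyses has been removed from the study as described in the protocol". SAP section 2.2 is also confined to efficacy: "All efficacy endpoints mentioned in the protocol have been removed and noted as changes to the planned analyses".

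**The concern.** Everyone receives ACTIMMUNE in 302 (Protocol 9.4.8), so the 301 arm is the only treatment distinction available. It is also a difference in exposure. Both 301 arms enter after 26 completed weeks of blinded treatment (Protocol 9.3.1 and 9.4.1). At 302 Baseline, prior-ACTIMMUNE subjects therefore have about 26 weeks on drug and prior-placebo subjects have none from 301. At Week 26 of 302 the exposures are about 52 and 26 weeks.

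A pooled antibody percentage by visit mixes these. It gives neither the rate after first exposure nor the prevalence after about a year, and its Baseline row shows only net change.

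Other safety tables have the same problem. Changes are measured from 302 Baseline (SAP 2.2.1), which is an on-drug value for one group and a pre-drug value for the other, so a pooled mean change can dilute a first-exposure effect such as raised transaminases. Adverse events ongoing from 301 count as baseline signs (Protocol 9.5.3.1.2), and flu-like symptoms may lessen with continued treatment (Protocol 9.2), so pooled event rates may understate those on first exposure. Long-term safety is the primary objective and, with efficacy removed, these tables are what the report consists of.

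**Working it through.** **Text comparison.** No planned figure is in dispute, so the main check sets the statements side by side.

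| Item | Protocol | SAP |
|---|---|---|
| Layers of presentation | Treatment received in 301, and overall (Synopsis) | Overall treatment (section 6 and the analysis sections) |
| Group definition | 301 treatment named | None; *overall treatment* and *treatment group* are undefined |
| Declared change | Not applicable | Efficacy only (sections 2.2 and 10) |

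The protocol sentence uses *overall* for the layer that is distinct from 301 treatment. Pooled is therefore the natural reading of the SAP phrase, though the SAP never says *only*.

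**Can the pooled Baseline row recover the split?** The documents give neither the 301 allocation nor antibody rates for this trial. The inputs below are assumptions:

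- f = fraction of subjects with prior placebo: 1/2 (1:1) or 1/3 (2:1 active to placebo)
- b = pooled positivity at 302 Baseline, all in prior-ACTIMMUNE subjects: 12%
- w = pooled positivity at Week 26: 20% (also tried at 12%)
- x = prior-placebo positivity at Week 26, the quantity wanted

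If Baseline positives may revert, x runs from max(0, (w − (1 − f))/f) to min(1, w/f). If every Baseline positive persists, the upper bound falls to (w − b)/f. The lower bound is 0 in every case shown, because all new positives could be in the prior-ACTIMMUNE group.

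| b, w | f | All persist: upper bound | Reversion allowed: upper bound |
|---|---|---|---|
| 12%, 20% | 1/2 | (0.20 − 0.12)/0.5 = 16% | 0.20/0.5 = 40% |
| 12%, 20% | 1/3 | 0.08/(1/3) = 24% | 0.20/(1/3) = 60% |
| 12%, 12% | 1/2 | 0/0.5 = 0% | 0.12/0.5 = 24% |
| 12%, 12% | 1/3 | 0/(1/3) = 0% | 0.12/(1/3) = 36% |

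The last two rows show that a flat pooled percentage settles the question only if no antibody reverts. Otherwise it is compatible with anything from no new antibody to a rate of 24% or 36% on first exposure.

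**Context from the label** (Protocol 17.2, label section 6.3). Non-neutralizing antibodies developed in 8 of 33 treated patients, 24.2% (Clopper-Pearson 95% CI 11.1-42.3%), and in 0 of 38 healthy volunteers (CI 0-9.3%). No neutralizing antibodies were detected in patients. The label warns that such rates depend on assay and underlying disease, so these figures show only that the question is a real one.

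**The case against.** The strongest reply is that pooling is inferred. In SAP 9.1 and 9.2.1 the phrase is overall treatment *received*. Since treatment in 302 alone distinguishes nobody, this could mean the sequence across 301 and 302. The denominator rule in SAP 6 and the shift tables in 9.2 refer to a treatment group, which presupposes groups. SAP 4.2 adds that "All final, planned analysis identified in the protocol and in this SAP will be performed", so silence need not mean deletion. Column layout is normally fixed in the table shells, and those pages cannot be read. The protocol rule is a single synopsis sentence, the study is descriptive, immunogenicity data are listed by subject, and the numbers above are hypothetical.

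Much of this is fair as a limit on certainty. The wording is ambiguous, the shells might show the split, the ranges are algebra on assumed inputs, and a reader could derive the answer by hand from the listings. The conflict remains. No readable SAP text defines a group by 301 treatment, and a general reference to protocol analyses does not override a specific presentation rule. The move to an abbreviated safety report explains dropping efficacy; it does not explain dropping a split of the safety tables. Even on the charitable reading, the programmer has no defined column variable and the same correction is needed.

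**Conclusion.** The concern holds. As worded, the SAP departs from the protocol's presentation rule for all summaries, and the change is not declared. The effect is on interpretation of the descriptive safety tables, most plainly the antibody table; no test or error rate is involved. Under the stated assumptions, the first-exposure antibody rate at Week 26 is left uncertain over a range 16 to 60 percentage points wide when pooled positivity rises from 12% to 20%. The true width depends on the 301 allocation and on rates the documents do not give. The change should be made. Confidence is medium, because the planned-tables pages could not be checked.

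**What to change.** In SAP sections 6 and 9.2.1, and wherever the phrase recurs, replace *overall treatment* with *treatment received in HZNP-ACT-301 (ACTIMMUNE, placebo) and overall*. Use the same definition for *treatment group* in sections 6 and 9.2. If the split is being dropped on purpose, say so in SAP section 10 and give the reason.

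A useful addition, promised by neither document, is one antibody row within each 301 group: subjects negative at 302 Baseline who become positive during 302, over those negative at 302 Baseline. Label it treatment-emergent for prior placebo and new in 302 for prior ACTIMMUNE.

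The cost is SAP wording, some extra table columns and one optional row, using 302 data already collected plus the 301 assignment. No protocol change or new sample is needed. The drawback is small cell counts in the added columns.

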6.1 Visit Windows

Subjects who withdraw from the study will have their data collected at the premature withdrawal (PW) visit assigned to the closest scheduled visit (either prior or post PW) where the data was scheduled to have been collected based on the protocol schedule of events. The data collected closest in time and date to protocol scheduled timing will be used for analysis.

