9.4.7.3 Details Concerning Timing and Dose Administration

All doses of study drug will be administered by SC injection. Subjects and/or their caregivers will be instructed on their individualized dosing volume and proper dosing techniques; they will also be instructed to administer the study drug on the right and left deltoid, anterior thigh, and upper and lower abdomen and to rotate the injection sites.

Subjects or their caregivers will also be instructed in safe handling and storage of used syringes and needles. The clinical staff will demonstrate proper technique for withdrawing the appropriate volume of study drug from the vial. When two vials are needed to achieve the dose, an equal volume should be removed from each vial. For example, if the dose should be 0.8 mL, then 0.4 mL should be withdrawn from each vial into separate syringes and two injections given. The injection site will be cleaned with an alcohol swab and allowed to air dry. About an inch of skin and fat tissue will be pinched between the thumb and forefinger, the needle will be inserted all the way into the pinched skin, and the entire volume of study drug will be injected under the skin.

The first dose of study drug is after the Baseline/Day 1 Visit and will be administered at home before bedtime according to the subject's TIW dosing schedule. Subjects and their caregivers will be instructed to administer study drug on an outpatient basis TIW before bedtime; and to adhere to a dosing schedule of Monday, Wednesday and Friday or Tuesday, Thursday, and Saturday for the duration of the study as agreed to by the clinic staff. Subjects and their caregivers will also be instructed concerning the use of acetaminophen, and/or ibuprofen, and/or diphenhydramine to alleviate injection site and study drug reactions (see [Table 9.1](#) for allowable doses).

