9.5.3.1.1 Definitions

Adverse Event: An AE is defined in 21 CFR 312.32(a) as any untoward medical occurrence associated with the use of a drug in humans, whether or not considered drug-related.

A TEAE is any adverse change from the subject's baseline condition, including any laboratory test value abnormality judged as clinically significant by the investigator, that occurs on or after the date of the first dose of study drug administered at home and throughout the duration of the clinical study, whether the AE is considered related to the treatment or not. Adverse events include the following types of occurrences:

- Adverse reaction: an adverse reaction means any AE caused by a drug. Adverse reactions are a subset of all suspected adverse events for which there is reason to conclude that the drug caused the event.
- Suspected adverse reaction means any AE for which there is a reasonable possibility that the drug caused the AE. Reasonable possibility means there is evidence to suggest a causal relationship between the drug and the AE. A suspected adverse reaction implies a lesser degree of certainty about causality than adverse reaction, which means any AE caused by a drug. Suspected adverse reactions are the subset of all AEs for which there is a reasonable possibility that the drug caused the event.
- Other medical experiences, regardless of their relationship to the study drug, such as injury, accidents, increased severity of pre-existing symptoms, apparently unrelated illness, and clinically significant abnormalities in clinical laboratory values, physiological testing, or physical examination findings.
- Reactions from drug overdose, abuse, withdrawal, sensitivity, an interaction with another drug or substance, or toxicity.

Serious Adverse Event (SAE): An AE is considered serious if, in the view of either the Investigator or Sponsor, it results in any of the following outcomes:

- Death. This includes any death that occurs during the conduct of a clinical study, including deaths that appear to be completely unrelated to the study drug (e.g., car accidents).
- Life-threatening adverse experience. An AE or suspected adverse reaction is considered life-threatening if, in the view of either the Investigator or the Sponsor, its occurrence places the subject at immediate risk of death. It does not include an AE or suspected adverse reaction that, had it occurred in a more severe form, might have caused death.

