2.2.1 Safety Endpoints

Adverse event and concomitant medication data will be summarized. Clinical laboratory safety data, vital sign data, echocardiogram data, and ECG interval data will be summarized with descriptive statistics for Baseline of HZNP-ACT-302, post-dose, and change from Baseline of HZNP-ACT-302 to post-dose values. Shift tables will be presented for clinical laboratory values and ECG categorical results from Baseline of HZNP-ACT-302 to each post-dose visit. Physical examination findings will be listed by subject. Results of immunogenicity testing will be presented in tabular format.

[figure not shown]

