5. ANALYSIS POPULATIONS

The following analysis populations are planned for this study:

- **Safety Population (SAFETY):** The Safety Population includes all subjects who receive at least one dose of open-label study drug after the Baseline Visit for HZNP-ACT-302. All analyses will be based on the Safety Population unless otherwise noted.

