6.3 Derived and Computed Variables

The following derived and computed variables have been initially identified as important for the analyses of Safety, Efficacy and Exploratory endpoints. It is expected that additional variables may be required. The SAP will not be amended for additional variables that are not related to the primary target or key secondary target variables. Any additional derived or computed variables will be identified and documented in the SAS programs that create the analysis files. If the SAP is not amended, further derivations related to primary and secondary target variables will be described in the CSR.

- 302 Baseline = The last non-missing measurement/assessment on the date of Week 26 Visit from HZNP-ACT-301. If this measurement is missing or otherwise unavailable, it will be the last non-missing measurement/assessment on or prior to first dose in HZNP-

ACT-302.

- 301 Baseline = The last non-missing measurement/assessment prior to first dose of Study in HZNP-ACT-301.
- Study Day = Assessment Date – Date of Enrollment + 1
- Change from Baseline = Value at Post-Baseline – Value at Baseline
- Concomitant Medication is defined as any medication a subject has received concurrently with study treatment.
- Prior Medication is defined as any medication or therapies initiated prior to date of first dose of study drug. Medications that are started prior to the date of first dose of study drug and continue after the first dose of drug are considered to be both prior and concomitant medications.
- Treatment-Emergent Adverse Event (TEAE) – A TEAE is any adverse change from the subject's baseline condition that occurs on or after the date of the first dose of study drug through the duration of the clinical study.
- Related TEAE – Any TEAE with a reported relationship to study drug of 'possibly related'.
- Compliance = Calculated as the percentage of the number of vials used divided by the expected number of vials used, where the number of vials used is the number of used vials returned.

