12. TABLES, LISTINGS, AND FIGURES

This section presents the list of shells for the planned Tables, Listings and Figures to be programmed in support of the planned analyses identified in the SAP. This section is intended to support the SAP and provides guidance on the programming specifications (shells) for the planned outputs and may be updated, independent of the SAP, with any updates appropriately documented, reviewed, and approved.

The following reporting conventions will be adopted for the presentation of study data. These conventions will enhance the review process and help to standardize the presentation with common notations.

General Reporting Conventions

- All tables and data listings will be developed in landscape orientation.
- Specialized text styles, such as bolding, italics, borders, shading, superscripted and subscripted text will not be used in tables and data listings unless they add significant value to the table, figure, or data listing.
- Only standard keyboard characters should be used in tables and data listings. Special characters, such as nonprintable control characters, printer-specific characters, or font specific characters, will not be used on a table, figure, or data listing. Hexadecimal character representations are allowed (e.g., μ , α , β).
- All titles will be centered on a page. The ICH numbering convention is to be used for all outputs.
- All footnotes will be left justified and at the bottom of a page.
- Missing values for both numeric and character variables will be presented as blanks in a table or data listing. A value of zero may be used if appropriate to identify when the frequency of a variable is not observed.
- All date values will be presented as ddmmmyyyy (e.g., 29AUG2011) format. A 4-digit year is preferred for all dates.
- If applicable, all observed time values will be presented by using a 24-hour clock HH:MM:SS format (e.g., 01:35:45 or 11:26). Seconds should only be reported if they were measured as part of the study.
- All tables and data listings will have the name of the program, the location, and a date stamp on the bottom of each output.

Population Summary Conventions

- Population sizes may be presented for each classification factor as totals in the column header as (N=xxxx), where appropriate.
- Population sizes shown with summary statistics are the samples sizes (n) of subjects with non-missing values.

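### SAP 6.1 lets Baseline be the closest visit for premature-withdrawal data, so early post-dose ECG, laboratory, vital-sign and immunogenicity values have no post-baseline row in by-visit tables

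*SAP*

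**What the plan says.** SAP 6.1 has two sentences on this. PW data are "assigned to the closest scheduled visit (either prior or post PW) where the data was scheduled to have been collected" under the protocol schedule. Then: "The data collected closest in time and date to protocol scheduled timing will be used for analysis". Neither sentence limits the candidate visits to those after Baseline.

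Baseline/Day 1 is a scheduled visit for every data type at issue (Protocol 2.1, 9.5.3.3 and 9.5.3.5 to 9.5.3.8).

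SAP 2.2.1 states that laboratory, vital-sign, echocardiogram and ECG interval data "will be summarized with descriptive statistics for Baseline of HZNP-ACT-302, post-dose, and change from Baseline of HZNP-ACT-302 to post-dose values". It also plans laboratory and ECG shift tables. Laboratory, vital-sign and ECG summaries are by visit (SAP 9.2, 9.3, 9.4), and antibody frequencies are by scheduled visit (SAP 9.2.1). For echocardiograms, SAP 9.4 promises summaries without saying they are by visit.

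SAP 6.3 takes the HZNP-ACT-302 Baseline from the Day 1 visit date. If that value is unavailable, "it will be the last non-missing measurement/assessment on or prior to first dose" in HZNP-ACT-302.

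**The concern.** A value measured after open-label dosing cannot be Baseline under SAP 6.3, yet SAP 6.1 can send it to the Baseline slot. There it competes with a record taken on the scheduled day, and loses. No legible SAP text then returns it to a post-baseline row.

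The subjects concerned are early withdrawers. On nominal days, someone who leaves inside the ranges below has had no earlier scheduled post-baseline assessment of that ECG, laboratory or vital-sign type. The PW value is then the only one that could put the subject into the change-from-baseline or shift table. For immunogenicity, a follow-up sample may still exist, so what is lost there is the PW result.

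Long-term safety is a primary objective (SAP 2.1.1), and efficacy analysis has been removed in favour of an abbreviated safety report (SAP 2.2, 8 and 10). These tables are therefore a main part of what will be reported.

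**Working it through.** The plan states no slotting cut-off, so there is no figure to reproduce. The scheduled days agree with 7 × week + 1: 29, 92, 183 and 197 for Weeks 4, 13, 26 and 28.

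**Rule applied.** Assign each PW day to the scheduled day with the smallest absolute difference. Visits are taken on their nominal days, and a Day 1 record is assumed to exist. The cut-off against Baseline is the midpoint between Day 1 and the next scheduled day for that data type.

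| Data type | Scheduled days (Protocol 2.1) | Midpoint with Baseline | PW days nearest Baseline |
|---|---|---|---|
| Labs, vital signs | 1, 29, 92, 183 | (1 + 29)/2 = 15, tie | 2–14 (13 days) |
| Immunogenicity | 1, 29, 92, 183, 197 | (1 + 29)/2 = 15, tie | 2–14 (13 days) |
| ECG | 1, 92, 183 | (1 + 92)/2 = 46.5, no tie | 2–46 (45 days) |
| Echocardiogram | 1, 183 | (1 + 183)/2 = 92, tie | 2–91 (90 days) |

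SAP 6.1 has no rule for the ties on Day 15 and Day 92.

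**Sensitivity.** If distance is measured to the edge of the ±3-day window, the last days nearest Baseline are 13 (labs, vital signs, immunogenicity), 44 (ECG) and 90 (echocardiogram).

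**Post-dose days only.** The Safety Population is "all subjects who receive at least one dose of open-label study drug after the Baseline Visit for HZNP-ACT-302", and "The first dose of study drug is after the Baseline/Day 1 Visit and will be administered at home before bedtime" (Protocol 9.4.7.3). The schedule is Monday/Wednesday/Friday or Tuesday/Thursday/Saturday. If Day 1 is a dosing day, which fits the planned two doses in the first week and escalation on Day 8, the first home dose falls on Day 3 or Day 4. With bedtime dosing, the first possible post-dose PW visit is Day 4 or Day 5. The affected days are then:

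- Labs, vital signs, immunogenicity: 14 − 4 + 1 = 11, or 14 − 5 + 1 = 10.
- ECG: 46 − 4 + 1 = 43, or 46 − 5 + 1 = 42.
- Echocardiogram mapped to Baseline: 91 − 4 + 1 = 88, or 91 − 5 + 1 = 87.

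**What happens to the value.** The Day 1 record is zero days off schedule, so the second sentence of SAP 6.1 selects it. SAP 6.3 separately bars the PW value from being Baseline. SAP 6.2 puts data not analysed under the plan in listings only.

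**The case against.** The best reply is that the SAP should be read as a whole. SAP 6.3 defines Baseline by date and change as post-baseline minus Baseline, and SAP 2.2.1 promises post-dose summaries, so Baseline is not a sensible home for a post-dose value. That is right about intent, but it names no other destination. Two programmers could follow the same text to different tables.

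A second reply is that the protocol labels the last treatment visit as Week 26 or PW, which suggests that PW data belong there. SAP 6.1 does not follow that label. It asks for the closest visit before or after PW, a comparison that would be pointless if every PW value went to Week 26.

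The third reply largely succeeds. A reader might infer that echocardiography is the worst case, with every post-dose PW echocardiogram up to Day 91 dropped because Week 26 is its only scheduled post-baseline visit. The documents do not support that as a certainty. SAP 9.4 says by visit for ECG but not for echocardiograms, and SAP 2.2.1 plans post-dose echocardiogram summaries. An early PW echocardiogram could be included without a visit slot.

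Finally, the planned-table content is not legible in this copy, and the shells "may be updated, independent of the SAP" (SAP 12). An end-of-treatment row may already exist, and its absence here cannot be counted against the plan.

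**Conclusion.** The point holds for the by-visit tables. As written, SAP 6.1 maps post-dose PW ECGs up to Day 46, and labs, vital signs and immunogenicity up to Day 14, to Baseline and leaves them without a post-baseline row. Echocardiograms up to Day 91 map the same way, but whether they are omitted is open.

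The day ranges are not risks. The documents give no withdrawal distribution, and the number of subjects affected may be zero. Nor do the documents support an inference that safety findings would be hidden. SAP 6.2 lists all collected data, and Protocol 9.5.3.1.1 counts as adverse events "clinically significant abnormalities in clinical laboratory values, physiological testing, or physical examination findings", so those reach the adverse event tables. The effect is on descriptive tables only.

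The result rests on nominal visit days, an available Day 1 record, a literal reading of SAP 6.1, and the legible text alone. It is worth correcting because the correction is cheap and the rule affects only early withdrawers.

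**What to change.** Amend SAP 6.1 along these lines, with a cross-reference to the 302 Baseline definition in SAP 6.3:

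*PW assessments taken after the first HZNP-ACT-302 dose are post-baseline and are never assigned to Baseline. They are summarised in an End of treatment (Week 26 or PW) row. A PW value also enters a by-visit row only if the subject has no record at that visit (not attended or not yet due), the PW day is at least as close to that visit as to Baseline, and that visit is the nearest of the post-baseline visits.*

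The row should cover labs, vital signs, ECG, echocardiogram and immunogenicity, including the laboratory and ECG shift tables. Add it only where the shells lack it.

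The wording settles both ties in favour of the post-baseline visit. An echocardiogram up to Day 91 appears only in the end-of-treatment row and is not labelled Week 26; from Day 92 it also enters Week 26. Merely excluding Baseline would instead label a Day 5 echocardiogram as Week 26.

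The cost is SAP wording and at most one row per table. The row mixes exposure durations, so the by-visit rows should stay alongside it.
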